Appendix 3.Pregnancy Precautions, Definition for Female of Childbearing
Potential, and Contraceptive Requirements

1) Definitions

a. Definition of Childbearing Potential

For the purposes of this study, a female born subject is considered of childbearing potential following the initiation of puberty (Tanner stage 2) until becoming post-menopausal, unless permanently sterile or with medically documented ovarian failure.

Women are considered to be in a postmenopausal state when they are ≥ 54 years of age with cessation of previously occurring menses for ≥ 12 months without an alternative cause.

Permanent sterilization includes hysterectomy, bilateral oophorectomy, or bilateral salpingectomy in a female subject of any age.

b. Definition of Male Fertility

For the purposes of this study, a male born subject is considered fertile after the initiation of puberty unless permanently sterile by bilateral orchidectomy or has medical documentation of permanent male infertility.

2) Contraception Requirements for Female Subjects

a. Study Drug Effects on Pregnancy and Hormonal Contraception

GS-4997 is contraindicated in pregnancy as a malformation effect is suspected, based on non-clinical data. In rats and rabbits, GS-4997 administration was associated with effects on embryo-fetal development at maternally toxic doses. This included total litter loss, increased resorptions and post implantation loss, reduced fetal weights, and visceral and skeletal malformations and variations. Embryofetal effects were observed in rats and rabbits at exposures (AUC24hr) that were 62- and 12-fold higher, respectively, than the GS-4997 steady state exposure in NASH subjects at the maximum human dose of 18 mg once daily. The NOELs for embryofetal development in rats and rabbits were 15 and 10 mg/kg/day, respectively. The exposure margins at these doses as compared to the maximum proposed human dose are 12 - and 3-fold, respectively.

Preclinical data indicate that GS-4997 is unlikely to reduce the exposure of hormonal contraceptives through induction of human drug metabolizing enzymes or drug transporters. This is supported by clinical DDI data, which demonstrated multiple doses of GS-4997 did not result in increased activity of CYP3A4 or P-gp based on plasma exposures of sensitive probe substrates (midazolam and digoxin). Similarly, preclinical and clinical data indicate GS-4997 is unlikely to cause a clinically relevant increase in the exposure of hormonal contraceptives through inhibition of drug metabolizing enzymes or drug transporters. Please refer to the latest version of the investigator's brochure for additional information.

b. Contraception Requirements for Female Subjects of Childbearing Potential

The inclusion of female subjects of childbearing potential requires the use of highly effective contraceptive measures. They must have a negative serum pregnancy test at Screening and a negative pregnancy test on the Baseline/Day 1 visit prior to randomization. Pregnancy tests will be performed at monthly intervals thereafter. Female subjects must agree to one of the following from Screening until 90 days after the last dose of study drug.

• Complete abstinence from intercourse of reproductive potential. Abstinence is an acceptable method of contraception only when it is in line with the subject's preferred and usual lifestyle.

Or

- Consistent and correct use of 1 of the following methods of birth control listed below.
 - Intrauterine device (IUD) with a failure rate of < 1% per year
 - Tubal sterilization
 - Essure micro-insert system (provided confirmation of success 3 months after procedure)
 - Vasectomy in the male partner (provided that the partner is the sole sexual partner and had confirmation of surgical success 3 months after procedure)
- The above described methods are considered preferred methods of highly effective contraception in this protocol.
 - Should female subjects wish to use a hormonally based method, use of a male condom by the female subject's male partner is required. Subjects who utilize a hormonal contraceptive as one of their birth control methods must have used the same method for at least three months prior to study dosing. Hormonally-based contraceptives permitted for use in this protocol are as follows:
 - Hormonal methods (each method *must* be used with a condom in the male partner)
 - Oral contraceptives (either combined or progesterone only)
 - Injectable progesterone
 - Implants of levonorgestrel
 - Transdermal contraceptive patch
 - Contraceptive vaginal ring

Female subjects must also refrain from egg donation and in vitro fertilization during treatment and until at least 90 days after the last dose of study drug.

3) Contraception Requirements for Male Subjects

It is theoretically possible that a relevant systemic concentration may be achieved in a female partner from exposure of the male subject's seminal fluid. Therefore, male subjects with female partners of childbearing potential must use condoms during treatment until 90 days after the last dose of study drug. Female partners of male study subjects should consider using one of the above methods of contraception as well.

Male subjects must also refrain from sperm donation during treatment and until at least 90 days after the last dose of study drug.

4) Unacceptable Birth Control Methods

Birth control methods that are unacceptable include periodic abstinence (eg, calendar, ovulation, symptothermal, post-ovulation methods), withdrawal (coitus interruptus), spermicides only, and lactational amenorrhea method (LAM). Female condom and male condom should not be used together.

5) Procedures to be Followed in the Event of Pregnancy

Subjects will be instructed to notify the investigator if they become pregnant at any time during the study, or if they become pregnant within 90 days of last study drug dose. Subjects who become pregnant or who suspect that they are pregnant during the study must report the information to the investigator and discontinue study drug immediately. Subjects whose partner has become pregnant or suspects she is pregnant during the study must report the information to the investigator. Instructions for reporting pregnancy, partner pregnancy, and pregnancy outcome are outlined in Section 7.6.2.1.

Appendix 4. Child-Pugh-Turcotte (CPT) Classification of the severity of cirrhosis

		POINTS	
	1	2	3
Encephalopathy	None	Grade 1-2 (medication-controlled)	Grade 3-4 (medication-refractory)
Ascites	None	Mild/Moderate (diuretic-responsive)	Severe (diuretic-refractory)
Bilirubin (mg/dL)	< 2	2-3	> 3
Albumin (g/dL)	> 3.5	2.8-3.5	< 2.8
INR	< 1.7	1.7-2.3	> 2.3

Note: if the either ascites or encephalopathy is "none" because the patient is taking medication which has controlled the symptoms, the scoring should be 2 points (not 1 point).

CPT score is obtained by adding the points for each parameter

CPT class is scored as: $A = 5$

B = 7-9 points

C = 10-15 points

# LIST OF ABBREVIATIONS

AE	adverse event
AH	alcoholic hepatitis
ALT	alanine aminotransferase
ASK1	Apoptosis Signal-regulating Kinase 1
AST	aspartate aminotransferase
AUDIT	Alcohol Use Disorders Identification Test
BAP	Biomarker Analysis Plan
bpm	beats per minute
BLQ	below the limit of quantitation
BMI	body mass index
CFR	Code of Federal Regulations
CI	confidence interval
CK-18	cytokeratin-18 fragment level
CPT	Child-Pugh-Turcotte
CSR	clinical study report
CTCAE	Common Toxicity Criteria for Adverse Events
DF	discriminant function
DMC	Data Monitoring Committee
eCRF	electronic case report form
ECG	Electrocardiogram
$\mathrm{ELF}^{\mathrm{TM}}$	enhanced liver fibrosis test
ET	early termination
FAS	full analysis set
GGT	gamma-glutamyl transferase
HbA1c	glycated hemoglobin
HBsAg	hepatitis B surface antigen
HCV	hepatitis C virus
HDL	high-density lipoprotein
Hgb	Hemoglobin
HIV	human immunodeficiency virus
HLGT	high-level group term
HLT	high-level term
HRS	hepatorenal syndrome
ICH	International Conference on Harmonization (of Technical Requirements for Registration of Pharmaceuticals for Human Use)
INR	international normalized ratio
IWRS	interactive web response system
LDL	low-density lipoprotein
LLT	lower-level term

LOCF	last observation carried forward
LOQ	limit of quantitation
LOXL2	serum lysyl-oxidase-like 2
LPS	Lipopolysaccharides
MedDRA	Medical Dictionary for Regulatory Activities
MELD	Model for End-Stage Liver Disease
mITT	modified Intent-to-Treat
mmHg	millimeters of mercury
РК	Pharmacokinetics
PKEX	pharmacokinetics study drug administration page
PLA	Placebo (to match selonsertib)
PRED	Prednisolone
PT	preferred term
Q1, Q3	first quartile, third quartile
QD	once daily
SADQ	Severity of Alcohol Dependence Questionnaire
SAP	statistical analysis plan
SBP	spontaneous bacterial peritonitis
SAE	serious adverse event
SD	standard deviation
SEL	Selonsertib (formerly GS-4997)
SOC	system organ class
SOW	statement of work
TEAE	treatment-emergent adverse event
TFLs	tables, figures, and listings
ULN	upper limit of normal
VLDL	very low-density lipoprotein
WBC	white blood cells
WHO	World Health Organization

# PHARMACOKINETIC ABBREVIATIONS

AUC tau	area under the concentration versus time curve over the dosing interval
C last	last observed quantifiable concentration of the drug in plasma
C max	maximum observed concentration of the drug in plasma
C tau	observed drug concentration at the end of the dosing interval
T last	time (observed time point) of C last
T max	time (observed time point) of C max
$\lambda_z$	terminal elimination rate constant, estimated by linear regression of the terminal elimination phase of the plasma concentration of drug versus time curve
t 1/2	estimate of the terminal elimination half-life of the drug in plasma, calculated by dividing the natural log of 2 by the terminal elimination rate constant ( $\lambda_z$ )
CLss/F	Apparent oral clearance after administration of the drug at steady state: $CLss/F = Dose/AUC_{tau}$ where "dose" is the dose of the drug (for selonsertib only)

# 1. INTRODUCTION

This statistical analysis plan (SAP) describes the statistical analysis methods and data presentations to be used in tables, figures, and listings (TFLs) for the final analysis for Study GS-US-416-2124 which will be conducted after all subjects complete their Week 24 study visit and/or Week 24 subject status form or prematurely discontinue from study. This SAP is based on Amendment 3 of the study protocol dated 04 August 2017 and the electronic case report form (eCRF). The SAP will be finalized before the database is finalized. Any changes made after the finalization of the SAP will be documented in the clinical study report (CSR).

## 1.1. Study Objectives

The primary objective of the study is:

• To evaluate the safety and tolerability of selonsertib in combination with prednisolone versus prednisolone alone in subjects with severe alcoholic hepatitis (AH)

The secondary objectives of the study are:

- To assess changes in hepatic synthetic function (liver biochemistry, Model for End-Stage Liver Disease [MELD] score, Child-Pugh-Turcotte [CPT] score, the Lille model, and Maddrey's Discriminant Function [DF]);
- To assess mortality at 28 days and at 8, 12, and 24 weeks;
- To determine the incidence of liver transplantation;
- To determine the incidence of hepatorenal syndrome (HRS);
- To determine the incidence of infection;
- To assess length of initial hospital stay.

The exploratory objectives of the study are as follows:

# 1.2. Study Design

This is a Phase 2, randomized, double-blind, proof-of-concept study evaluating the safety, tolerability, and biological activity of selonsertib in combination with prednisolone versus prednisolone alone in subjects with severe, histologically-confirmed AH. Subjects are 18 to 70 years of age, with a history of excessive alcohol consumption (average of > 40 g/day of alcohol for women and > 50 g/day of alcohol for men); AST  $\geq$  50 and  $\leq$  400 U/L; ALT  $\leq$  300 U/L; AST/ALT ratio  $\geq$  1.5; onset of jaundice within the past 3 months; a screening Maddrey DF score  $\geq$  32 and  $\leq$  60; and a MELD score  $\leq$  30. Subjects consented under Amendment 1 of the study protocol will qualify for the study and be stratified based on the screening MELD score calculated using central laboratory results while all other subjects will qualify for the study and be stratified based on the screening MELD score calculated using local laboratory results. All analyses of laboratory values for efficacy and safety will be based on central laboratory (ie, Covance Laboratories, Inc.) results except for the specific cases for Lille and MELD scores described in Section 3.6.1.

Up to 120 subjects will be randomized to obtain 100 subjects with histologically-proven severe AH who are evaluable for the Full Analysis Set (FAS). Subjects meeting the study's entry criteria will be randomly assigned within strata (screening MELD < 25 or  $\geq$  25) to one of the following 2 treatment groups in a 1:1 ratio:

- Group A (n = 50-60): Selonsertib 18 mg QD + Prednisolone 40 mg QD for 28 days
- Group B (n = 50-60): Selonsertib Placebo QD + Prednisolone 40 mg QD for 28 days

The screening and randomization phase will take approximately 2 weeks; and study drugs will be administered for a total of 28 days. Subjects will be followed for a total of 24 weeks (ie, 20 weeks following last dose of study drug); with the exception of subjects who have a biopsy that is consistent with an alternative etiology for liver disease; and those with positive serologies for HBsAg, HIV, or hepatitis C virus (HCV)-these subjects will be followed to last dose date plus 30 days for safety evaluation. Laboratory results (serum chemistry, hematology, coagulation tests), calculation of MELD, CPT (includes clinical assessments of hepatic encephalopathy and ascites) and Maddrey DF scores, and collection of vital signs, alcohol consumption, and concomitant medications and assessment of HRS and infections will be performed at screening, Day 1, Weeks 1, 2, 3, 4, 6 and 8 and every 4 weeks thereafter through Week 24. Lille score will be calculated at Weeks 1, 2, 3, and 4. Adverse events will be collected through the last dose date of any study drug plus 30 days. Serious adverse events (SAEs) not related to study endpoints will be collected up to last dose date + 30 days. Adverse events and SAEs related to study endpoints (eg, deaths, infections, and HRS) will be collected throughout the study. Insulin, lipid profiles, and weight will be collected at screening, baseline, and at Weeks 4, 12, and 24. HbA1c will follow the lipid schedule, but will not be collected at screening or Week 4. Investigator assessment of 12-lead electrocardiograms (ECG) will be collected at screening, baseline and at Weeks 4 and 8. Pregnancy testing for women of childbearing potential will be performed at screening (serum), Day 1, and every 4 weeks throughout the study.

ELF score will be collected at baseline, and at Weeks 4, 12 and 24; and the Alcohol Use Disorders Identification Test (AUDIT) and Severity of Alcohol Dependence Questionnaire (SADQ) will be administered at screening to determine levels of alcohol use and dependence on alcohol.

Single PK samples will be collected on Day 1 and at Weeks 1, 2, and 4. Subjects participating in the PK substudy will have a full profile collected between Weeks 1 and 3 of the study.

#### 1.3. Sample Size and Power

The number of subjects was chosen based on clinical experience with other similar proof of concept studies. PPD

# 2. TYPE OF PLANNED ANALYSIS

# 2.1. Data Monitoring Committee Analyses

An independent external Data Monitoring Committee (DMC) that included 2 hepatologists and a PhD statistician convened prior to study start, once 20 subjects had completed Study Day 28, and every 3 months thereafter to review the progress of the study and perform interim reviews of safety data in order to protect subject welfare and preserve study integrity.

The DMC additionally evaluated trial stopping criteria, based on an unblinded review of safety data, and recommend early termination of the trial if there was a > 20% higher percentage of subjects in the SEL + PRED group than in the PLA + PRED group with: 1) Grade 3 or higher treatment-emergent, treatment-related adverse event(s) of a specified type, excluding evaluation of liver function, that led to premature discontinuation of selonsertib/placebo; 2) Death on/prior to Study Day 28; 3) Lille score > 0.85 while on study drug; or 4) post-baseline selonsertib/placebo laboratory stopping criteria (ie, ALT or AST > 500 U/L, ALT or AST > 5 x baseline [confirmed on repeat testing], and/or total bilirubin > 3 x baseline or nadir [confirmed on repeat testing]). See Section 7.1.7 of this SAP.

The DMC was to recommend to the sponsor whether the nature, frequency, and severity of adverse effects associated with study treatment warranted the early termination of the study in the best interests of the participants, whether the study should continue as planned, or whether the study should continue with modifications.

The DMC's roles and responsibilities and the scope of analysis provided to the DMC were provided in a mutually agreed upon charter, which defined the DMC membership, meeting logistics, and meeting frequency.

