7.5. Toxicity Management

Treatment-emergent toxicities will be noted by the Investigator and brought to the attention of the Medical Monitor. Whether or not considered treatment-related, all subjects experiencing AEs must be monitored periodically until symptoms subside, any abnormal laboratory values have resolved or returned to baseline levels or they are considered irreversible, or until there is a satisfactory explanation for the changes observed.

Administration of all study drugs may be discontinued due to a clinical or laboratory adverse event. Subjects are allowed to take one study drug and not the other.

Prednisolone may be dose-reduced or interrupted at the discretion of the investigator (e.g. due to new-onset, severe sepsis or diabetes mellitus that cannot adequately be controlled). Prednisolone should be discontinued in subjects with a Lille Score ≥ 0.56 at Day 7 (null responders); these subjects may continue GS-4997/placebo treatment. Except in Lille Score null responders, restarting prednisolone may be considered if the reason for interruption has resolved or become adequately controlled in the opinion of the investigator within 7 days of prednisolone interruption. Any decision to restart prednisolone must be reviewed with the Medical Monitor.

There is no option for GS-4997/placebo dose reduction, but GS-4997/placebo may be interrupted due to drug-related toxicity (see below). If GS-4997/placebo is interrupted, it may be restarted on

a case by case basis if the reason for interruption has resolved or become adequately controlled in the opinion of the investigator within 7 days of GS-4997/placebo interruption. Any decision to discontinue or restart GS-4997/placebo must be reviewed with the Medical Monitor.

Subjects who meet any of the following criteria must stop GS-4997/placebo

- Laboratory Criteria (based on central laboratory data):
 - Total bilirubin > 3x Baseline/Day 1 or nadir (confirmed by immediate repeat testing)
 - ALT and/or AST > 5x Baseline/Day 1 (confirmed by immediate repeat testing), unless the elevation is thought by the Principal Investigator to be secondary to an etiology other than GS-4997-related, drug-induced liver injury (e.g. infection).

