 - AST and/or ALT >500 U/L should trigger prompt (within 24-48 hours) evaluation of patients for consideration of GS-4997/placebo discontinuation. If patients with AST and/or ALT >500 U/L are continued on study drug, they must be monitored closely with repeat PE and laboratory evaluation at least 3 times per week.
- Lille score > 0.85 at any time point (eg, on/after first scheduled post-Baseline/Day 1 visit) while on study drug (base on central or local laboratory data)
- Any Grade 3 or higher AE assessed as possibly or likely related to GS-4997

Other than in the case of the liver enzymes noted above, Grade 3 or 4 clinically significant laboratory abnormalities should be confirmed by repeat testing as soon as practical to do so (Medical Monitor needs to be notified), and preferably within 3 calendar days of receipt of the original test results.

Clinical events and clinically significant laboratory abnormalities will be graded according to the Common Terminology Criteria for Adverse Events (CTCAE) Version 4.03, which can be found at http://evs.nci.nih.gov/ftp1/CTCAE/CTCAE_4.03_2010-06-14_QuickReference_8.5x11.pdf.

When restarting investigational medicinal product following resolution of the adverse event, the investigational medicinal product should be restarted at full dose following discussion with the Medical Monitor.

Any questions regarding toxicity management should be directed to the Medical Monitor.

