8.11. Data Monitoring Committee

An independent, external Data Monitoring Committee (DMC) that includes two hepatologists and a PhD statistician will convene prior to study start, once 20 subjects have been treated for 28 days and every 3 months thereafter to monitor the study for safety events including SAEs, death, premature discontinuation of treatment for AEs, Grade 3 and higher AEs, Grade 3 and higher treatment-emergent laboratory abnormalities, and individual subject stopping criteria for GS-4997/placebo study drug (see Section 7.5). The DMC will also evaluate (based on an unblinded review of safety data) and recommend early termination of the trial if there is a > 20% higher percentage of subjects in the GS-4997/prednisolone group than in the prednisolone alone group with: 1) Grade 3 or higher, treatment-emergent, treatment-related adverse event(s) of a specific type (excluding evaluation of liver function) where GS-4997/Placebo was prematurely withdrawn; 2) death on/prior to Study Day 28; 3) Lille score > 0.85 while on study drug; 4) any of the post-baseline GS-4997/placebo laboratory stopping criteria (ie, ALT or AST > 500 U/L that led to discontinuation of GS-4997/placebo, ALT or AST > 5x Baseline/Day 1 [confirmed on repeat testing]; or total bilirubin > 3 x Baseline/Day 1 or nadir [confirmed on repeat testing]).

The DMC will provide recommendations to Gilead on whether the nature, frequency, and severity of adverse effects associated with study treatment warrant the early termination of the study in the best interest of the participants, whether the study should continue as planned, or the study should continue with modifications. The DMC may also provide recommendations as needed regarding study design.

The DMC's specific activities will be defined by a mutually agreed charter, which will define the DMC's membership, conduct and meeting schedule.

While the DMC will be asked to advise Gilead regarding future conduct of the study, including possible early study termination, Gilead retains final decision-making authority on all aspects of the study.

9. **RESPONSIBILITIES**

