#### 7.1.7. Analysis of Adverse Events of Interest

Post-baseline criteria (up to last dose date of SEL/PLA [confirmatory values may be collected after the last dose date]) will be used to screen for individual subjects who should stop dosing with SEL/PLA study drug. DMC members used these same criteria to determine whether there was a > 20% higher percentage of subjects in the SEL + PRED group than PLA + PRED group with events in any of the 4 categories (ie, DMC trial stopping criteria).

SEL/PLA study drug stopping criteria for an individual subject is as follows:

- 1) Grade 3 or higher, treatment-emergent, treatment-related adverse event(s) of a specific type (excluding evaluation of liver function) that leads to discontinuation of SEL/PLA
- 2) Death on/prior to Study Day 28
- 3) Lille Score > 0.85 while on study drug
- 4) Any of the post-baseline SEL/PLA laboratory stopping criteria:
  - ALT or AST > 500 U/L
  - ALT or  $AST > 5 \times Baseline/Day 1$  (confirmed on repeat testing)
  - Total Bilirubin > 3 x Baseline/Day 1 or Nadir (confirmed on repeat testing)

The baseline/Day 1 value will be defined as the last available measurement on/prior to first dose of SEL/PLA, and the nadir value will be defined as the lowest postbaseline value prior to the current value being assessed. A listing will be provided that includes each individual subject who met any of the SEL/PLA stopping criteria.

Prednisolone study drug stopping criteria in an individual subject is as follows: Subjects with a Week 1 Lille score  $\ge 0.56$  will be prematurely discontinued from PRED. This criteria is the same as the secondary efficacy parameter Lille null response (Lille score  $\ge 0.56$  at Week 1) which is described in Section 6.2.4 of this SAP.

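### The SAP's selonsertib/placebo stopping criterion 4 counts any on-drug ALT or AST above 500 U/L; protocol 8.11 counts it only when it led to discontinuation

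*SAP*

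**What the plan says.** **Protocol 8.11** has the DMC recommend termination if the percentage of subjects meeting any one of four criteria is more than 20% higher on GS-4997 plus prednisolone than on prednisolone alone. In criterion 4, the 500 U/L item reads "ALT or AST > 500 U/L that led to discontinuation of GS-4997/placebo".

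**Protocol 7.5** puts the 500 U/L item in a list headed "Subjects who meet any of the following criteria must stop GS-4997/placebo". The item itself asks for something less: "evaluation of patients for consideration of GS-4997/placebo discontinuation", within 24 to 48 hours. It then provides for those who stay on drug: "If patients with AST and/or ALT >500 U/L are continued on study drug, they must be monitored closely", with examination and laboratory tests at least three times a week.

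**SAP 2.1** restates the DMC rule in the past tense, with criterion 4 given as "laboratory stopping criteria (ie, ALT or AST > 500 U/L, ALT or AST > 5 x baseline [confirmed on repeat testing" and the bilirubin item following. The discontinuation condition is absent.

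**SAP 7.1.7** says its criteria "will be used to screen for individual subjects who should stop dosing with SEL/PLA study drug". Criterion 4 is "Any of the post-baseline SEL/PLA laboratory stopping criteria", and its first item is again ALT or AST above 500 U/L with no condition. The section adds that "DMC members used these same criteria to determine whether there was a > 20% higher percentage". Its window runs to the last SEL/PLA dose.

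**SAP Appendix 1** plans Table 15.11.2.4.2 (subjects meeting any stopping criterion), Table 15.11.2.4.4 (laboratory stopping criteria) and Listing 16.2.7.6.4.2, whose title limits the 500 U/L values to time on study drug but not to values that led to stopping.

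**The concern.** The two documents define the same item differently, and the difference is one of substance. Under the protocol, a subject above 500 U/L who is evaluated and kept on drug has not met criterion 4. Under SAP 7.1.7 that subject has met it and is described as someone who should have stopped.

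Safety is the primary endpoint. A stopping-criteria table that mixes an evaluation trigger with actual stops can overstate how many subjects met a protocol-defined criterion. It can also make correct conduct under 7.5 look like a missed stop. SAP 7.1.7 says the DMC used the same criteria, so the SAP also leaves it uncertain which definition lay behind the DMC's outputs.

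**Working it through.** The check is mainly a comparison of texts. The plan gives no figure for this item that could be reproduced.

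**Is the omission just shorthand?** Qualifiers in each account:

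| Item | Protocol 8.11 | SAP 2.1 | SAP 7.1.7 |
|---|---|---|---|
| Criterion 1: related AE, Grade 3 or higher | SEL/PLA withdrawn | led to discontinuation | leads to discontinuation |
| ALT/AST > 5 x baseline | confirmed | confirmed | confirmed |
| Bilirubin > 3 x baseline or nadir | confirmed | confirmed | confirmed |
| ALT/AST > 500 U/L | led to discontinuation | none | none |

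Every other qualifier in these rows survives; only the one on 500 U/L is lost. This does not look like general abbreviation. Read literally, one unconfirmed on-drug value is enough under the SAP.

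**Direction.** Subjects above 500 U/L who stopped because of it are a subset of all subjects above 500 U/L on drug. The SAP count is therefore at least as large as the protocol count in each arm. The effect on the difference between arms could go either way.

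**How easily the threshold is reached.** Inputs are the local screening limits in protocol 4.2 and 4.3: AST at most 400 U/L, ALT at most 300 U/L, AST/ALT at least 1.5.
- AST: 500/400 = 1.25-fold from the cap.
- ALT: the highest value compatible with the AST cap and the ratio is 400/1.5 = 266.7 U/L, and 500/266.7 = 1.875-fold.
- The 500 U/L and 5 x baseline limits coincide at 500/5 = 100 U/L. Above that baseline, 500 U/L is reached first.

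These are extreme entry values, and Day 1 values may differ. They show that the 500 U/L item can be met well short of a fivefold rise. They say nothing about frequency.

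**Size per subject.** One added subject is 1/60 = 1.7 points or 1/50 = 2.0 points. The tables use the Safety Analysis Set, so the figure nearer 60 is the more relevant; 50 is the FAS target. A subject who already meets another criterion adds nothing to the any-criterion table.

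**Could the broader definition have tripped the DMC rule?** This is an illustration on assumed inputs: the 20% margin read as percentage points, equal true rates in both arms, a protocol-defined criterion 4 rate of 5% to 10%, and 0 to 10 further points of continued subjects above 500 U/L. Exact two-binomial calculation:

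| Per arm | Excess subjects needed | Chance with no added cases | Chance with 10 added points |
|---|---|---|---|
| 10 | 3 | 0.7% to 3.0% | 5.6% to 7.8% |
| 50 | 11 | at most 0.03% | 0.17% to 0.43% |
| 60 | 13 | at most 0.01% | 0.07% to 0.21% |

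Ten per arm corresponds to the first review, after 20 subjects, if the arms were balanced. At full size the effect is negligible.

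**The case against.** The strongest defence is that the SAP wording has a basis in the protocol and errs on the cautious side. Protocol 7.5 does list 500 U/L under a must-stop heading. Protocol 7.5.1 sends every confirmed value above 500 U/L to independent adjudication whether or not drug was stopped. SAP 7.1.7 concerns events of interest and describes a screen, so showing all such values there is reasonable. That supports keeping them all in the listing. It does not support counting them as criterion 4, because the item's own words in 7.5 allow continuation and 8.11 is explicit.

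Only the titles of the two tables are given, so separate rows or a footnote cannot be ruled out. That stands, and it is why the point is about what the outputs can do as defined.

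Four stronger inferences are tempting, and the documents do not support them:
- *That a reader could not separate continued from stopped subjects.* Listings 16.2.5.1 (drug administration), 16.2.5.2 (premature discontinuations) and 16.2.7.5.1 (AEs leading to discontinuation) allow it by cross-reading. Protocol 7.1.3 requires a laboratory abnormality leading to discontinuation to be recorded as an AE.
- *That SAP 7.7 is false in declaring no deviations.* It speaks of protocol-specified safety analyses. The 500 U/L qualifier sits in the DMC section (8.11), and protocol 8.8 specifies no stopping-criteria table.
- *That the DMC applied the wrong rule.* The charter and DMC outputs are not among the documents.
- *That the protocol-defined count is 0 or 1.* SAP 4.2.2 names one subject, who stopped for ALT above 5 x baseline, but that paragraph serves adherence and need not list everyone.

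**Conclusion.** The mismatch is real and confined to one item. SAP 7.1.7 criterion 4, and the account of the DMC rule in SAP 2.1, omit the discontinuation condition in protocol 8.11 and sit badly with the permission to continue in 7.5. The final stopping-criteria outputs can be inflated, never deflated, by 1.7 to 2.0 points per affected subject in a planned arm.

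The number affected and the effect on the arm difference are not in the documents. No trial decision still to come is shown to depend on the point, and no change in the conclusion follows from it. Severity is the lowest.

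The SAP states that it is based on protocol Amendment 3. The amendment number of the supplied protocol is not visible in its text, so the comparison assumes they are the same version. SAP 4.2.2 also lists the bare 500 U/L item, but its adherence rule applies only to subjects who stopped SEL/PLA, so adherence is unaffected.

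**What to change.** 1. In SAP 7.1.7, restrict the 500 U/L item of criterion 4 to values that led to discontinuation of SEL/PLA, and use that definition in Tables 15.11.2.4.2 and 15.11.2.4.4.
2. Keep all on-drug values above 500 U/L in Listing 16.2.7.6.4.2, and add a column showing whether SEL/PLA was continued or stopped.
3. Check the DMC charter and outputs, then state in SAP 2.1 which definition they used. If it was the unqualified one, note it there as a departure from protocol 8.11.

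The cost is SAP wording, one definition shared by two tables, one listing column and a look at the charter and outputs. No new data are needed: ALT and AST values, the reason for stopping SEL/PLA and the action taken for each AE are already collected.
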